8.5 Futility Criteria

As this is a phase 1 study intended to determine the recommended dose of APR-246 in combination with venetoclax and rituximab in a limited number of patients with RT, futility criteria based on efficacy are not included.

8.6 Safety

Safety data will be summarized for the safety population. These data will include AEs, laboratory parameters, electrocardiogram, and physical exam findings. AE terms will be coded using the Medical Dictionary for Drug Regulatory Activities (MedDRA)®, version 22.0 or higher. AEs will be summarized by SOC, preferred term, severity, and relationship to treatment. SAEs, deaths, and AEs leading to early discontinuation of study treatment will be summarized. Laboratory parameters will be summarized by maximum NCI-CTCAE version 5.0 severity grade and also by change from pre-treatment to scheduled time points using descriptive statistics. Laboratory parameter listings will include the normal ranges for each parameter. Each value will be classified as falling above, below, or within the normal range.

Only SAEs related to study screening procedures from the time of signing informed consent and AEs from the time of first dose of APR-246, throughout study enrollment, and up to 30 days after last dose of study treatment are to be collected. Data summaries will include only TEAEs, defined as events occurring at the start of APR-246 infusion in the monotherapy lead-in or Cycle 1, Day 1 up to and including 30 days after last dose of study treatment.

8.7 Efficacy

CR rate will be summarized for the safety and EE patients as the proportion (%) of patients with CR. In addition to presenting the CR rate, its associated exact 95% CI will also be presented.

DOR is defined as the time from the date when criteria for response are met to the date of disease

progression or death due to any cause, whichever occurs first. Patients alive with no disease progression will have their DOR censored at the date of the last clinical assessment. The duration of CR will be summarized by providing the median DOR together with associated 95% CI, using Kaplan-Meier methodology.

ORR will be summarized in number (%) of patients in each category of responses and ORR will be analyzed by using a similar method to the one used for the CR rate. ORR is defined as the number of patients who achieve CR and partial remission (PR) measure per Lugano criteria (see [Appendix V](#)).

Survival data are collected at treatment and follow-up periods. Patients will be followed until death or withdrawal of consent from the study, whichever occurs first.

OS is defined as the number of days from the first day of treatment to the date of death due to any cause. Kaplan-Meier methodology will be utilized.

PFS is defined as the time from the first day of treatment to disease progression or death due to any cause, whichever occurs first. If neither event occurs, PFS will be censored at the date of the last clinical assessment. Kaplan-Meier methodology will be utilized.

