- k. Serum chemistry must include sodium, potassium, magnesium, phosphorus, chloride, CO_2 , blood urea nitrogen (BUN), creatinine, glucose, calcium, albumin, total protein, total bilirubin, AST, ALT, alkaline phosphatase, uric acid, and lactate dehydrogenase (LDH).
- l. Cockcroft-Gault method (see [Appendix I](#)).

- m. Serum or urine beta-human chorionic gonadotrophin (β hCG) must be performed within 7 days prior to study treatment initiation in female patients of childbearing potential.
- n. Standard 12-lead ECGs in triplicate at screening, Days 1-2 of APR-246 Lead-In, Days 1, 8 and 15 of Cycle 1 and on Days 1 of each subsequent cycle with patient in a semi-recumbent position prior to APR-246 administration. Please consult [Table 19](#) for ECG collection schedule.
- o. Please consult Section [7.4](#) for PK sample collection schedule.
- p. Patients discontinuing treatment should complete their end of treatment visit within approximately 28 days of their last dose of APR-246. Physical exam, weight, vital signs, ECOG PS, clinical toxicity assessment, concomitant medications, hematology, serum chemistry, ECG and disease assessment should be performed, if feasible.
- q. Long-term follow up can be done remotely (e.g., via telephone, via local practitioner or via review of medical records). Assuming there is no withdrawal of consent, patients who stop study treatment for any reason (e.g., toxicity, transition to stem cell transplant, disease progression) will continue long term follow-up (see Section [6.9](#)). If a patient is removed from the study due to unacceptable AEs, the event(s) will be followed until resolution or stabilization.
- r. AE description, grade and start date and resolution date should be documented.
- s. Historical record can be used from up to 1 year in the past.
- t. Testing mandatory. Patients with prior exposure to hepatitis B (i.e., positive anti-hepatitis B core antibody) must demonstrate hepatitis B PCR to be negative during screening period and undergo prophylaxis and monitoring for hepatitis B according to institutional guidelines. Reflex PCR testing is required if serology is positive.
- u. PD analyses as described in [Table 18](#) and Section [8.8](#).

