6.10 Long-Term Follow-Up

Long-term follow-up can be done remotely (e.g., via telephone, via local practitioner or via review of medical records). After a patient is removed from the study, the patient will be followed until death. If a patient has withdrawn consent from study, then follow-up has to cease on the date when consent for study was withdrawn. Off-treatment data on OS will be updated every 3 months or until death or withdrawal of consent for study participation, whichever occurs first. If a patient is removed from the study due to unacceptable AEs, the event(s) will be followed until resolution or stabilization of the AE. Patients who respond and discontinue study treatment for reasons other than disease progression should have response assessments and survival should be collected every 2 months until disease progression or death, whichever occurs first. After disease progression, data for survival should be collected every 3 months until death or withdrawal of consent for study participation.

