7.2 Efficacy Assessments

7.2.1 Complete Remission Rate

CR rate will be defined as the proportion of patients who achieve CR. The rate of MRD-negative CR is defined as the proportion of patients who achieve MRD-negative CR.

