7.2.2 Duration of Response

Duration of response (DOR) will be measured from the time of initial response to disease progression or death.

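### DOR and CR rate have no stop at transplant or other subsequent anticancer therapy, so remission time and PR-to-CR upgrades that follow such therapy can be counted for the study regimen

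*Combined protocol and SAP*

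**What the plan says.** **CR rate.** Section 7.2.1: "CR rate will be defined as the proportion of patients who achieve CR". Section 8.7: "CR rate will be summarized for the safety and EE patients as the proportion (%) of patients with CR". Neither sets a cut-off at new therapy.

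**ORR.** Section 8.7: "ORR is defined as the number of patients who achieve CR and partial remission (PR", per Lugano. Again there is no cut-off.

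**DOR.** Section 7.2.2: "Duration of response (DOR) will be measured from the time of initial response to disease progression or death". Section 8.7 adds the censoring rule: "Patients alive with no disease progression will have their DOR censored at the date of the last clinical assessment". The start of another treatment is neither an event nor a reason to censor. The synopsis and Section 8.3.2 define DOR in the same way.

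**Follow-up after treatment.** Footnote q of the schedule of assessments (Section 6.1) lists "transition to stem cell transplant" among the examples of why a patient may stop, and says that long-term follow-up then continues. Section 6.10: "Patients who respond and discontinue study treatment for reasons other than disease progression should have response assessments", and these data "should be collected every 2 months until disease progression or death, whichever occurs first". The synopsis adds withdrawal of consent as an end point. Neither place ends response assessment at new therapy. Section 4.10.1 ends study treatment when a new treatment for the disease starts, but says nothing about response follow-up.

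**PFS, for comparison.** Section 7.3 censors a patient who starts subsequent therapy without reported progression at the last evaluable tumor assessment before that therapy. Section 8.7 does not repeat this rule for PFS, and no response endpoint has one.

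**The concern.** The plan foresees transplant, collects response data after it in exactly the patients likely to receive it, and gives no rule for separating those data from the effect of the study regimen. Followed as written, two things can happen:

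- A responder who goes to transplant keeps accruing DOR for as long as the transplant holds the disease.
- A PR at the end of study treatment that becomes a CR after transplant enters the numerator of the CR rate.

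Both effects run upward, and both fall in the safety population, which Section 8.2 makes the main population for efficacy. CR rate and DOR serve the secondary objective of preliminary clinical activity (Section 3.2). Efficacy data are also one input to the optimal dose (Section 5.1.5), and Section 8.9 relates exposure to signs of efficacy. A rule left open until data are in hand could also be chosen with knowledge of the results.

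**Working it through.** **1. Denominators.** Section 8.1 gives up to 48 patients. This reproduces as 3 × 6 (escalation) + 10 (at the MTD) + 2 × 10 (Dose Levels 1 and 2) = 48. The relevant denominators are 6 (one cohort), 6 + 10 = 16 (one expanded dose level) and 48 (all).

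**2. One patient under the stated rules.** Suppose PR at study month 3, transplant at month 5 and progression at month 20.

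| Endpoint and rule | Result |
|---|---|
| DOR, Section 8.7 | event at 20 − 3 = 17 months |
| PFS, Section 7.3 | censored at or before month 5 |
| PFS, Section 8.7 | event at month 20 |
| DOR with the Section 7.3 rule applied | censored at or before 5 − 3 = 2 months |

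The same patient has a DOR of 17 months beside a PFS follow-up of at most 5 months, so the two endpoints cannot be read together.

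**3. CR rate.** Each PR-to-CR upgrade after later therapy adds 1/n: 1/6 = 16.7 points, 1/16 = 6.25 points, 1/48 = 2.1 points. Example at n = 16, with assumed counts: 2 CRs before later therapy give 2/16 = 12.5% (exact 95% CI 1.6 to 38.3). Counting two upgrades gives 4/16 = 25.0% (7.3 to 52.4).

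**4. ORR.** An upgraded patient was already a PR. With an assumed 6 responders of 16, ORR is 6/16 = 37.5% (15.2 to 64.6) whether or not the upgrade counts.

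**5. DOR.** The documents give neither a DOR median nor a transplant rate, so this is illustration only. Assume exponential DOR with median m without transplant, so λ = ln 2 / m. A fraction f of those still in response 3 months after response is transplanted, and their hazard is then multiplied by h. For t > 3 the curve as written is

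S(t) = exp(−3λ) × [(1 − f) exp(−λ(t − 3)) + f exp(−λh(t − 3))],

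and the reported median solves S(t) = 0.5. Censoring at transplant returns m, because transplant is unrelated to prognosis in this model.

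For m = 6, λ = 0.1155 and exp(−3λ) = 0.7071, so the bracket must equal 0.5/0.7071 = 0.7071. With f = 0.3 and h = 0.5, put x = exp(−λ(t − 3)/2). Then 0.7x² + 0.3x = 0.7071 gives x = 0.8134 and t = 6.58. The other cells follow in the same way:

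| m (months) | f | h = 0.5 | h = 0.25 |
|---|---|---|---|
| 6 | 0.05 | 6.1 | 6.1 |
| 6 | 0.10 | 6.2 | 6.3 |
| 6 | 0.30 | 6.6 | 7.0 |
| 6 | 0.50 | 7.1 | 8.1 |

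A separate simulation put transplant 2 months after response in 20% or 40% of those still in response, with a later median of 12 or 24 months. For m = 6 it gave 6.5 to 6.8 months (20%) and 7.1 to 8.2 months (40%), against 6.0 with censoring. Over base medians of 4 to 9 months, the inflation was about 0.3 to 2.8 months.

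**The case against.** **ORR.** A reader might infer that ORR is inflated too, and that every response first reached after later therapy adds 17 points in a cohort of 6. The documents do not support this. Section 6.10 schedules off-treatment response assessments only for patients who have already responded. Non-responders have no scheduled response assessment after the end-of-treatment visit, which falls within 28 days of the last dose (Section 6.9). A new response could enter ORR only if later therapy began before that visit. The text does not exclude this, but it is a narrow opening. The demonstrated rate effect is on CR alone.

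**Certainty.** A reader might also infer that later remissions will be credited. Section 6.7 speaks of response to study treatment and ties assessments to numbered cycles, and Section 6.10 does not say that an upgrade after transplant counts as best response. The supported statement is that it can be counted. For DOR, the issue is a prolonged response, not a new one.

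**Size.** Transplant appears once, as an example in a footnote, and the population has relapsed or refractory disease with a cited median survival of 3 to 11 months (Section 2.1). The transplant rate may be low, and the DOR shift would then be small.

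**Choice of rule.** Following DOR to progression or death whatever therapy follows is a recognised option, and censoring at transplant may be informative. This stands as a reason to report both versions. It does not justify leaving the rule unstated and different from Section 7.3.

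**Weight.** The endpoints are secondary, without a power calculation or an efficacy futility rule. The recommended dose is defined by apoptosis in the monotherapy cycle at or below the MTD or the maximum dose. This limits the consequence and stands.

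**Conclusion.** The point holds for DOR and CR rate. Under the stated rules, DOR can include remission time maintained by transplant or later therapy, and a PR that becomes a CR afterwards can count for the study regimen, while Section 7.3 treats the same event differently for PFS. It does not hold for ORR by this route.

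The CR-rate effect is 17, 6 or 2 points per upgraded patient at n = 6, 16 or 48, and the number of such patients is unknown. The DOR effect rests on assumed values. A 6-month median is reported as about 6.6 to 8.1 months with 30-50% of responders transplanted at month 3 and a later hazard ratio of 0.25 to 0.5, but as about 6.1 months with 5%. The consequence is for the interpretation of preliminary activity in a descriptive phase 1 study. A clarification is worthwhile because it costs little.

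**What to change.** In Section 8.7, with the synopsis and Section 7.2 aligned:

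- Determine best response for the CR rate, and for ORR for consistency, from assessments before the start of any subsequent anticancer therapy, including transplant or cellular therapy.
- Censor DOR at the last evaluable tumor assessment before that therapy, as Section 7.3 does for PFS.
- Report DOR without that censoring as a sensitivity analysis, because censoring at transplant may be informative.
- Carry the Section 7.3 rule into the PFS text of Section 8.7, so that the two sections agree.

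The cost is a few sentences and one extra table. No visit or treatment rule changes. The start date of new therapy is already needed for the PFS rule in Section 7.3 and for ending adverse-event collection under Section 7.1.2.1. The remaining weakness, possibly informative censoring, is made visible by showing both analyses.

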8.8 Pharmacodynamic Analysis

PD analysis will be conducted using flow cytometry of circulating CLL/RT cells before and after treatment with APR-246 during monotherapy and the first day of combination treatment ramp-up to assess viability and apoptosis. Descriptive statistics (mean, standard deviation, CV% mean, geometric mean, CV% geometric mean) will be utilized to compare the post- and pre-treatment samples and the differences at each dose cohort level will be tested for relationship to dose.

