Study Design	
This is a phase 1, open-label study to determine the pharmacologically active dose range of APR-246 in combination with venetoclax and rituximab in patients with Richter's Transformed NHL (RT) and to select a recommended dose for further development. The study includes a dose escalation design (Figure 1). It is preceded by a brief APR-246 monotherapy lead-in to establish a baseline pharmacokinetic (PK) / pharmacodynamic (PD) profile after intravenous (IV) dosing in each patient and to obtain APR-246 PK after a single dose of APR-246 administered orally (PO). The recommended dose will be based on the safety, tolerability, PK and PD profile of APR-246 in combination with venetoclax and rituximab therapy in patients with RT. Once the recommended dose of APR-246 in combination with venetoclax and rituximab is established, further explorations in expansion arms may be pursued following a protocol amendment.
 
Patients with RT will receive APR-246 administered IV at the assigned cohort dose with standard doses of venetoclax and rituximab. Dose escalation will proceed in a standard 3 + 3 dose escalation design.
 <pre>graph TD; A[Monotherapy Lead-In: D1-7 APR-246 IV Dose X: D1 APR-246 500 mg PO: D2] --> B[Cycle 1: D1-35 APR-246 IV Dose X D1, 8, 15 Venetoclax PO Ramp Up]; B --> C[Cycle 2 and beyond: D1-28 APR-246 IV Dose X D1, 8, 15 Venetoclax PO 400 mg/day Rituximab 375 mg/m² (Day 2 Cycle 2), 500 mg/m² Day 2 Cycles 3-7]; C --- X[X = assigned cohort dose]</pre>

Figure 1: Clinical Trial Schema

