Statistics	
This is a phase 1, open-label study to determine the pharmacologically active dose range of APR-246 in combination with venetoclax and rituximab and to select a recommended dose for further development.
 
The recommended dose of APR-246 in combination with venetoclax and rituximab will be defined as the dose determined to be producing the greatest level of cellular apoptosis in circulating peripheral blood malignant cells in the monotherapy portion. Dose escalation will be stopped when either the MTD or the intended maximum dose of the study is reached.

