administered starting at Cycle 8 for up to a total of 24 cycles. Cycle 1 will consist of 35 days. Cycles 2 and beyond will be 28 days. The safety assessment (DLT) period begins at the start of treatment and extends to the end of Cycle 3.

Patients with RT will receive APR-246 administered IV at the assigned cohort dose with standard doses of venetoclax and rituximab. Dose escalation will proceed in a standard 3 + 3 dose escalation design.

The intended three dose levels of APR-246 are: 1.5 g/day, 3.0 g/day, and 4.0 g/day administered as an IV infusion over 6 hours. The dose escalation will proceed until a pharmacologically active dose level is achieved. It will be stopped if the maximum tolerated dose (MTD) is reached at a dose level below the maximum planned dose of 4.0 g/day. For the determination of MTD the following rules will be applied:

- Three patients will be enrolled to Dose Level 1.
- If 0 patients out of 3 experience a DLT at Dose Level 1 (1.5 g/day of APR-246), the dose will advance to the next level (Dose Level 2, 3.0 g/day).
- If 1 of the first 3 patients at Dose Level 1 experiences a DLT, 3 additional patients will be recruited and treated at the same dose level (1.5 g/day of APR 246).
- If ≥ 2 patients out of 3-6 patients in a cohort experience a DLT at Dose Level 1 (1.5 g/day of APR-246), the study will temporarily discontinue enrollment and the Data Review Team (DRT) will consider further enrollment and possible dose/schedule adjustments.
- If < 2 patients out of 6 experiences a DLT at Dose Level 1 (1.5 g/day), dose escalation will proceed to the next cohort level (Dose Level 2, 3.0 g/day).
- For each cohort, if there are 0 DLTs in the first 3 patients enrolled, the cohort will advance to the next level. If there is 1 DLT in the first 3 patients enrolled to a cohort, the cohort will enroll an additional 3 patients. If there are ≥ 2 DLTs in a cohort, the prior lower dose level will be declared the MTD.
- If there are ≤ 1 DLT in the first 3 patients enrolled at Dose Level 3, 4.0 g/day APR-246, the study will enroll 3 additional patients at Dose Level 3. If there are ≤ 1 DLTs in 6 patients enrolled at Dose Level 3, 4.0 g/day APR-246 will be declared the MTD.

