5.1.5 Recommended Dose of APR-246

The recommended dose of APR-246 in combination with venetoclax and rituximab represents the dose of APR-246 at or below the maximum intended dose, or the MTD, that results in the greatest apoptosis of circulating malignant cells in the monotherapy cycle.

The MTD of APR-246 will be defined as the dose at which <2 out of 6 patients experience DLT during the defined safety assessment period after administration of APR-246 in combination with venetoclax and rituximab. Up to 10 additional patients may be enrolled at the MTD, and at prior dose levels, to confirm the confidence at that dose level.

A DRT consisting of the Medical Monitor, Site Principal Investigators, and other clinical research personnel that the Sponsor may deem appropriate, will hold Data Review Meetings (DRMs) on an

interim basis at a frequency dependent on study accrual. At these meetings, the DRT will review any AEs, DLTs, and any available PK and PD data and make recommendations regarding the optimal dose of APR-246. All accumulated safety data will be discussed during DRMs. The optimal dose of APR-246 will be based upon the MTD and upon all accumulated safety data, PK/PD data, and preliminary efficacy data.

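### Section 8.8 tests PD differences for a dose relationship without adjusting for the pre-dose value, and the greatest-apoptosis comparison carries no interval for each dose level

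*Combined protocol and SAP*

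**What the plan says.** Section 8.8, repeated in the synopsis, describes flow cytometry of circulating CLL/RT cells before and after APR-246. On analysis it says: "Descriptive statistics (mean, standard deviation, CV% mean, geometric mean, CV% geometric mean) will be utilized to compare the post- and pre-treatment samples". The only inferential step is the dose test, in which, by the plan's wording, "the differences at each dose cohort level will be tested for relationship to dose". It names no test, scale, covariate or significance level. Arithmetic and geometric summaries are both listed, so the scale of the difference is open.

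The recommended dose is defined through the same endpoint. Section 5.1.5 caps the choice at the MTD or the highest planned dose and, within that cap, takes the one "that results in the greatest apoptosis of circulating malignant cells in the monotherapy cycle". The synopsis (Statistics) says "the dose determined to be producing the greatest level of cellular apoptosis in circulating peripheral blood malignant cells in the monotherapy portion", and its Recommended Dose paragraph repeats the rule. None of the three gives an interval, a margin or a rule for near-ties.

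Two other places describe a broader basis. The synopsis (Study Design) says: "The recommended dose will be based on the safety, tolerability, PK and PD profile of APR-246 in combination with venetoclax and rituximab therapy". Section 5.1.5 closes with: "The optimal dose of APR-246 will be based upon the MTD and upon all accumulated safety data, PK/PD data, and preliminary efficacy data".

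**The concern.** PD is the first primary endpoint in Section 8.3.1, and finding the recommended dose is the primary objective. A pre-dose sample is scheduled for every patient. The plan uses it only by subtraction, which amounts to fixing the coefficient of post on pre at 1. When the correlation is moderate, subtraction adds baseline noise to the outcome and the dose test loses power that a covariate would recover from the same blood samples.

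The second part concerns reporting. Levels may hold as few as 3 patients. A ranking by greatest apoptosis without intervals does not show whether the top level is distinguishable from the others.

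**Working it through.** **Cohort sizes.** Section 8.1 gives 3 to 6 patients per level, up to 10 more at the MTD and, if Dose Level 3 is the MTD, up to 10 more at Levels 1 and 2. The stated maximum reproduces: 3 × 6 + 3 × 10 = 48. Levels can therefore hold from 3 to 6 + 10 = 16 patients. On dose levels, Section 4.1 says: "The intended three dose levels of APR-246 are: 1.5 g/day, 3.0 g/day, and 4.0 g/day administered as an IV infusion over 6 hours". The synopsis states that no power calculation was made, so there is no planned PD figure to reproduce.

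**Assumptions, none from the documents.** Normal data on the analysis scale, pre and post SD both 1, rho from 0.3 to 0.9, two-sided 5% trend test.

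**Residual variance.**
- Change score: 2(1 − rho).
- Baseline-adjusted: 1 − rho².
- Ratio, adjusted to change: (1 + rho)/2.

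| rho | change | adjusted | ratio | extra patients the change score needs |
|---|---|---|---|---|
| 0.3 | 1.40 | 0.91 | 0.65 | 1/0.65 − 1 = 54% |
| 0.5 | 1.00 | 0.75 | 0.75 | 33% |
| 0.7 | 0.60 | 0.51 | 0.85 | 18% |
| 0.9 | 0.20 | 0.19 | 0.95 | 5% |

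The direction does not depend on equal SDs. In general the change-score variance exceeds the adjusted variance by (SD_pre − rho × SD_post)², which is never negative. The size does depend on them, and the formula is large-sample: it ignores the degree of freedom spent.

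**Trend power, by simulation** (20,000 or more trials per setting; true rise of 0/0.6/1.0 SD over the three levels). Entries are change score → baseline-adjusted.

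| Patients per level | rho 0.3 | rho 0.5 | rho 0.7 | rho 0.9 |
|---|---|---|---|---|
| 3/3/6 | 19% → 24% | 26% → 29% | 38% → 39% | 81% → 78% |
| 6/6/6 | 29% → 38% | 37% → 44% | 57% → 61% | 96% → 95% |
| 6/6/16 | 40% → 54% | 53% → 62% | 73% → 78% | 99% → 99% |
| 16/16/16 | 66% → 83% | 80% → 89% | 95% → 97% | 100% → 100% |

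A separate rerun agreed to within about 2 points.

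**Choice of the highest level.** For the same rise and 6/6/6 patients, the truly best level has the highest mean in 70% → 75% of trials at rho 0.3 and 74% → 77% at rho 0.5. Over the cohort sizes tried, the gain at these correlations was about 2 to 6 points. With no dose effect, 3/6/16 patients and rho 0.5, the levels come out highest in about 38%, 34% and 28% of trials. Baseline adjustment does not change that, because it comes from cohort size and from taking a maximum.

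**Why a single slope must not supply the ranking.** A linear term in log dose is monotone, so its highest fitted value is always at 1.5 g or 4.0 g. With no dose effect (3/6/16) it picks 50/0/50%. When Level 2 is truly best (0/1.0/0.5 SD), it picks Level 2 in 0% of trials, against 81% for the highest cohort mean.

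**The case against.** Several counter-arguments are sound.

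- A reader might infer that the baseline sample is wasted. It is not: a change score uses it, only less efficiently. Calling the differences raw also goes too far, since geometric summaries leave a log scale possible.
- The gain depends on an unknown correlation. Quoting only rho 0.3 to 0.5 would flatter the case. At 0.9 there is essentially no gain, and with 12 patients a small loss.
- The cohorts are sequential and not randomised. If baselines differ systematically between levels, the change score and the adjusted analysis can target different contrasts, and neither is automatically right. This is a reason to prespecify one and report both.
- A reader might infer that the Section 8.8 test, or noise in PD alone, sets the dose. The documents do not support that. No section links the trend test to the selection; the MTD or maximum intended dose caps the choice; and the synopsis (Study Design) and the end of Section 5.1.5 bring in safety, tolerability, PK and, in 5.1.5, preliminary efficacy.
- An exploratory phase 1 PD analysis without a power target need not be optimal. That is fair, but the improvement here needs no new samples.

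What remains is a less efficient test in most plausible settings, a ranking without stated precision, and definitions of the recommended dose that do not agree.

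**Conclusion.** The point holds as one of efficiency and reporting. As worded, the Section 8.8 dose test is less precise than a baseline-adjusted test of the same samples by a factor of (1 + rho)/2 in residual variance, that is 0.65 to 0.95 over assumed rho of 0.3 to 0.9. With 6/6/16 patients and a 1 SD rise, power goes from 40% to 54% at rho 0.3, from 53% to 62% at 0.5 and from 73% to 78% at 0.7, with nothing gained at 0.9. These sizes rest on assumed correlation, SDs and effects.

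It would be wrong to conclude that baseline adjustment cures the instability of picking the highest level; it adds only a few points. Intervals for each level do not remove that instability either, but they make it visible. The definitions of the recommended dose conflict on the role of PD, and the documents do not say which governs.

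**What to change.** 1. **Section 8.8 and the synopsis:** replace the test of differences by a test of dose in a model of the post-dose value (log or logit scale) on the pre-dose value and dose. Keep the change-score result as a sensitivity analysis, because the cohorts are sequential. Name the post-dose sample that enters the model, since Section 7.4 schedules several.
2. **Section 5.1.5 and the synopsis (Statistics and Recommended Dose):** for the greatest-apoptosis comparison, report baseline-adjusted estimates with 95% CIs for each dose level, with dose as a category. Level 2 can then rank highest, and it is visible when levels cannot be separated. Do not take the ranking from a single linear log-dose slope.
3. **Reconcile** the greatest-apoptosis definition with the synopsis (Study Design) and the last sentence of Section 5.1.5. Which basis governs is for the sponsor to decide.

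The cost is wording only, with no extra samples or visits. The statistical price is one degree of freedom for the covariate, which matters only when about 12 patients are available and the correlation is very high.
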